Describe the procedures required for this study

Evaluation

1. Every subject evaluated for this protocol will receive a clinical interview by a psychiatrist or psychologist, be administered the Center for Epidemiologic Studies Depression Scale (CES-D) and the 24-item Hamilton Rating Scale for Depression (HRSD), and have a SCID performed by a trained rater. If a subject has a diagnosis of Major Depressive Disorder (MDD) or Dysthymia, he/she will be informed of this and educated about the availability of treatments for depression. If a subject is not interested in depression treatment and/or prefers to begin with an experimental treatment for slowing and depression, he/she will be offered participation in the present study provided their HRSD \leq 25 and there is no suicidal ideation present. Severe MDD (i.e., HRSD \geq 25) and/or the presence of significant suicide risk (e.g., suicidal ideation, clinician judgement that there is significant risk of suicide) are exclusions for this study.

Patients with Depression NOS will be educated that as yet, there are no FDA-approved treatments for their condition. Based on the extant data supporting the efficacy of antidepressants for MDD and Dysthymia, they will be informed that antidepressant treatment would be a very reasonable option for their condition. These potential subjects will be offered the option of being referred out for depression treatment, and it will be clarified that L-DOPA is not as yet a treatment for MDD. Thus, all potential participants in this study must state their preference not to be treated with a standard treatment for depression.

- 2. Participants signing informed consent will have documentation of vital signs, medical history (including history of head injury, stroke, hypertension, cardiac disease, thyroid disease, other medical conditions, surgeries, hospitalizations, and current medications), physical exam, urine drug screen, CBC, chemistries and electrolytes, thyroid profile, vitamin B12 and folate levels, urine analysis, standing/supine systolic/diastolic BP, and ECG.

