- 11. The radiochemistry laboratory and PET suite staff will be in frequent communication regarding the status of preparation of the research subject (such as placement of venous line) and the progress of the radiotracer synthesis. As scan time approaches, the subject will be placed in a supine position on the camera table and will have vital signs (blood pressure and heart rate) obtained. Head will be positioned and a headholder will be used to decrease head movement during the scan.
- 12. Baseline scan: A low dose CT transmission scan is then obtained prior [11C] raclopride administration. At the end of the transmission scan, a maximum of 14 mCi of [11C] raclopride will be injected intravenously. The dose of [11C] raclopride, diluted in a 10 cc syringe, will be given as a single bolus over a period of 30 seconds. [11C] raclopride will be prepared by the central radio-ligand staff of the PET Center and will be administered by an approved Nuclear Medicine physician (Drs. [name], [name], or [name]). Study physicians will be present for all radiotracer injections. All study physicians have New York State Medical license and have had extensive training and experience with these types of PET studies. [11C] raclopride will be synthesized and tested for purity and sterility according to our standard procedure. The injected dose of [11C]-raclopride for each scan will not exceed 14 mCi, and lower amounts will be permitted. The study physician or Nuclear Medicine physician will evaluate the reconstructed PET image in order to ensure tracer uptake in the brain and will inform the radiochemist if there is a lack of expected uptake in the brain. All subjects will be monitored by the study physician at the time of injection and a study physician or nurse will be present in the PET suite.

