- 13. Post-treatment scan: As close to the end of the 3 week study as possible (based on PET scheduling), subjects will undergo their post treatment scan. We will follow standard procedures for measuring L-DOPA-induced changes in synaptic dopamine levels set forth in PET studies of PD patients. Subjects will be given 75mg carbidopa/300mg L-DOPA approximately 1.5 hours before scanning. Subjects in week 3 of the protocol are taking 450mg LDOPA per day (150mg three times daily), so the 300mg administered prior to the post-treatment PET scan will constitute 300mg of their usual 450mg daily dose on the scan day. A low dose CT transmission scan is obtained prior to intravenous administration of 14mCi [11C] raclopride (or less). The start of tracer injection will be timed to coincide with the time of onset of L-DOPA effects (approximately 60-90 minutes following oral dose). Thus, the 60 minute PET scanning session will occur from 90 minutes to 150 minutes following L-DOPA dosing in all subjects. At the completion of the scan the IV catheter will be removed, and the subject will be evaluated (including mental status and vital signs) by a study physician. Vital signs, and physical exam will be performed prior to discharge from the PET suite.
- 14. We are aware that the scanning dose of 300mg given at once approximates but may not match the CNS effects of subchronic dosing with 150mg tid. However, this method has the advantages of being consistent with imaging studies of PD patients in which L-DOPA doses are typically 250-300mg and avoiding confounding of Δ BPND estimates by downregulation of D2 receptors occurring with subchronic administration. Since nausea is a known side effect of L-DOPA, we will be particularly vigilant about monitoring for it. When nausea occurs patients generally feel warm and sick to their stomachs. It will likely

occur after PET scanning, but if vomiting were necessary, the MD would remove the subject from the scanner so that vomiting does not occur while supine. Removal from the scanner can occur immediately.

- 15. PET data will be reconstructed into images using the appropriate reconstruction protocols and filters. PET images will be coregistered to the MRI and regional time activity curves will be measured. Data will be fitted to pharmacokinetic models, and relevant pharmacokinetic parameters, including the percent of receptors engaged by dopamine, will be estimated based on the model fitting procedures.

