- 18. In selecting L-DOPA doses, we balanced appropriate safety concerns regarding the use of this medication in a novel patient population with the goal of causing a measurable effect. L-DOPA is an extremely well tolerated medication at doses < 600mg, which is substantially less than the doses often reached in the treatment of Parkinson's disease (900-1200mg). L-DOPA has been administered to healthy subjects in single dose studies and found to be well-tolerated. In Parkinson's disease, a recent clinical trial published in the New England Journal of Medicine randomized patients to receive 150mg, 300mg, or 600mg L-DOPA for 40 weeks. In the 150mg and 300mg L-DOPA treatment groups, the only side effects

observed that were different from placebo were headache and nausea. No dyskinesias or other neuropsychiatric effects were observed that were greater than the placebo group. In terms of effects, single-dose studies have reported significant effects on cognition and neural activation with L-DOPA doses as low as 100mg. Thus, we believe the 150-450mg dose range to be used in this study will be both safe and likely to produce an observable effect.

Assessments

- 19. Subjects are expected to have a screening/evaluation visit, PET/MRI scanning day (for those receiving imaging), and weekly visits from Week 0-3.
- 20. At baseline, we will record each subject's chief complaint, referral source, age of onset of mood and/or cognitive decline, number prior depressive episodes, age, sex, marital status, race and ethnicity, years of education, employment status and income, years of education, family history. We also will document medical history, physical exam, urine drug screen, CBC, chemistries and electrolytes, thyroid profile, vitamin B12 and folate levels, urine analysis, and ECG. Vital signs will be measured at baseline and monitored weekly throughout the study. The Cumulative Illness Rating Scale-Geriatric (CIRS-G) (112) will be filled out at baseline to measure chronic medical illness burden. Subjects' current physical pain will be assessed weekly using a 100mm Pain Visual Analog Scale (VAS) and used as a covariate in analyses of gait speed (113).

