There are many studies of chronic L-DOPA administration for the treatment of PD, since this drug has been used since the 1960s. Perhaps the most relevant recent study was a clinical trial published in the New England Journal of Medicine in 2004 (72). In this study 361 patients with PD were randomized to receive 150mg, 300mg, or 600mg L-DOPA for 40 weeks. In the 150mg and 300mg L-DOPA treatment groups, which are similar to the 100mg and 300mg treatment groups being used in the R61 Phase of this study, the only side effects observed that were different from placebo were headache and nausea. No dyskinesias or other neuropsychiatric effects were observed that were greater than the placebo group, and this study lasted 40 weeks as opposed to 3 weeks in the R61 Phase of this study. Despite these reassuring data, and recognizing that we include a different patient population, we will carefully assess subjects with new complaints to determine if they may be related to study drug and if there is a need for closer monitoring or change in study drug dosing.

- a. L-DOPA common side effects: In patients taking L-DOPA for the management of bradykinesia and freezing associated with PD, the most common side effects are dyskinesias (i.e., choreiform, dystonic, and other involuntary movements) and nausea.
- b. Other L-DOPA side effects: blood pressure changes, orthostasis, anorexia, dyspepsia, constipation, psychotic episodes (e.g., delusions, hallucinations), vivid dreams, and nightmares.

- c. Discontinuation Syndrome: A neuroleptic malignant-like syndrome (fever, akinetic crisis, rigidity, autonomic disturbances) has been reported following withdrawal of levodopa in patients with PD.

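### Standing/supine blood pressure is expressly ordered only once, before drug, so asymptomatic orthostasis on L-DOPA is not certain to be measured

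*Combined protocol and SAP*

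**What the plan says.** The Risks section lists, under L-DOPA effects (item 2b), "Other L-DOPA side effects: blood pressure changes, orthostasis". Subjects are 60 or older (Description of Subject Population) and are included if they walk below 1 m/s (Evaluation, item 4).

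Evaluation item 2 sets the work-up after consent. It begins "Participants signing informed consent will have documentation of vital signs, medical history" and ends its list with "thyroid profile, vitamin B12 and folate levels, urine analysis, standing/supine systolic/diastolic BP, and ECG". Vital signs and standing/supine pressure are thus two separate entries in one sentence. Subjects return the following week for eligibility review, so this precedes any dosing.

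The orders that apply on drug are:

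- Assessments item 20: "Vital signs will be measured at baseline and monitored weekly throughout the study".
- PET Scanning item 11, general scan preparation: "the subject will be placed in a supine position on the camera table and will have vital signs (blood pressure and heart rate) obtained".
- PET Scanning item 13, after the post-treatment scan: "the subject will be evaluated (including mental status and vital signs) by a study physician", and then "Vital signs, and physical exam will be performed prior to discharge from the PET suite".

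The exploratory aim includes tolerability, and Clinical treatment item 17 says the design can assess tolerability at 150, 300 and 450 mg. The statistical analysis plan section does not mention blood pressure.

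**The concern.** A postural drop is found by comparing a lying with a standing reading. The plan obtains that comparison before drug but does not require its counterpart once L-DOPA has started, so the pre-drug value has no guaranteed on-drug comparator.

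The population makes this worth attention. The Background section links slow gait to falls, and Clinical treatment item 18 calls this a novel patient population for the drug. The fall precautions in the Risks section concern the gait test, with staff beside the subject, whereas the drug is taken up to three times a day outside the clinic. Dyskinesia, which the Assessment Instruments section does not expect at these doses, has its own weekly on-drug instrument (UPDRS questions 32 and 33). Orthostasis, also a named risk, has none.

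At stake are the completeness of the tolerability description and the chance to notice a drop in a subject who reports nothing. Subjects who do well may also elect to continue L-DOPA after the study, and measured postural data would inform that choice.

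**Working it through.** The plan gives no figure to reproduce. The check is a count of express orders, followed by what a count of affected subjects could show.

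**Step 1. Orders side by side.**

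| Time | Place in protocol | Order | Posture stated |
|---|---|---|---|
| Work-up, before drug | Evaluation, item 2 | Vital signs, and separately standing/supine BP | Standing and supine |
| Baseline and weekly | Assessments, item 20 | Vital signs | None |
| Each scan, before tracer | PET Scanning, item 11 | BP and heart rate | Supine |
| After post-treatment scan | PET Scanning, item 13 | Vital signs, physical exam | None |

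Express standing/supine orders: 1 before drug, 0 at Weeks 1 to 3, 0 after the post-treatment scan. The PET rows apply to the imaging subset only.

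**Step 2. Does the weekly order absorb the postural one?** Item 20 repeats most of the Evaluation item 2 list, leaves out standing/supine BP, and then gives the vital-signs sentence. That could mean the postural reading was folded into vital signs, or that it was a one-off. Evaluation item 2, which keeps the two apart, favours the second reading but does not settle it. PET item 11 does not settle it either, because it describes a subject already on the camera table and not a clinic visit.

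**Step 3. Dose and timing of readings that could be added.**

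- Weekly: Assessments item 22 places gait and processing-speed tests at 1 pm, about 4 hours (4 × 60 = 240 minutes) after the morning dose, which is 150 mg under the scheduled titration. A postural reading placed before the gait test would share that timing. The documents give no clock time for weekly vital signs.
- After the post-treatment scan: the 60-minute scan starts 90 minutes after dosing, so a reading falls from about 90 + 60 = 150 minutes. The dose is 300 mg at once, and 300/150 = 2 times any scheduled single dose. The subject has just been lying down for an hour.

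**Step 4. What a count could say.** Inputs from the Summary of Experiences to Date: 36 participants, 8.3% drop-out, and df 24 for the change in raclopride binding.

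- Completers: 0.083 × 36 = 2.99, so 3 drop-outs and 36 − 3 = 33.
- Analysable scan pairs: 24 + 1 = 25 (scans performed may be more).
- With 0 events in n, the exact two-sided 95% upper limit is 1 − 0.025^(1/n).
- n = 33: 1 − 0.025^(1/33) = 0.106, or 10.6%.
- n = 25: 1 − 0.025^(1/25) = 0.137, or 13.7%.

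These limits assume every completer or scanned subject has a reading, and they bound only drops present when the reading is taken. I give no probability of detecting a case: it would need a true rate that the documents do not supply, plus perfect detection, which a reading 4 hours after dosing cannot promise.

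**The case against.** The strongest reply is that weekly vital signs may well have included standing readings. The document is an IRB summary form, where silence on posture is weak evidence that none was measured. That stands: the point concerns what the text requires, not what staff did.

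Second, symptomatic orthostasis is well covered. There is a weekly side-effect scale, enquiry at each visit, dose reduction, withdrawal rules and a commitment to assess new complaints and consider closer monitoring. On scan day there are a physician evaluation, an exam before discharge and an escort. This stands in full and is why the gap is narrow.

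Third, the protocol offers tolerability support. In the 40-week Parkinson's disease trial, at 150 and 300 mg, "the only side effects observed that were different from placebo were headache and nausea". The Risks section adds older case studies of depressed patients without Parkinson's disease at 400 to 1200 mg, with few side effects reported, and 16 healthy older adults given a single 200 mg dose, with mild nausea alone. The Description of Subject Population also excludes a history of cardiovascular disease and uncontrolled coronary risk factors (the criteria table does not repeat this), and unstable medical illness is excluded in both places. All of this lowers the expected risk. None of it, as described, shows that standing pressure was measured, and the two Parkinson's arms stop short of 450 mg.

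Fourth, weekly readings could not attribute a drop to a dose, because dose rises with week in a fixed sequence and there is no control. That is right, so the benefit is safety screening.

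A reader might infer that blood pressure goes unchecked on drug, that orthostasis is wholly unmonitored, or that weekly readings were taken lying down. The documents support none of these: vital signs are ordered weekly, symptoms are sought at every visit, and the supine posture belongs to the PET table.

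**Conclusion.** The point holds as a limited gap in required measurement. One standing/supine reading is expressly ordered, before drug, and none on drug, in older subjects chosen for slow gait and given a drug for which the protocol itself lists orthostasis. What may be missed is a measured or asymptomatic postural drop. Aims 1 and 2 are untouched and no planned estimate changes.

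The conclusion rests on reading vital signs and standing/supine pressure as separate items, as Evaluation item 2 lists them. If the clinic's weekly vital signs routinely included a standing reading, the matter reduces to one of wording. Confidence is medium for that reason. It is a cheap improvement worth making, and nothing here shows that any subject was harmed.

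**What to change.** In Assessments item 20, repeat the Evaluation item 2 standing/supine measurement at Week 0 before drug and at Weeks 1 to 3 before the gait test, recording time since the last dose. In PET Scanning item 13, add one such reading after the post-treatment scan and before discharge. Report the number of subjects with a drop beyond a threshold set in advance by the sponsor's clinicians. Present it as safety screening and not as a dose effect, and state that dose and week are confounded and that there is no control.

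The cost is a few minutes per visit for staff already taking vital signs, using a procedure already in the protocol. The limitation to accept is that a reading about 4 hours after dosing may miss the peak.

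The continuation report says R61 interventions are complete, so these edits cannot alter that phase. For R61, if postural readings were taken, report them. If not, add one sentence saying that orthostasis was ascertained only through symptoms and routine vital signs. The Lay Summary refers to a separate R33 submission, which is not available here. Carry the measurement into that protocol unless it is already there.

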I am submitting an annual continuation without modifications

Division & Personnel

Division

What Division/Department does the PI belong to?

Psychiatry

Within the division/department, what Center or group are you affiliated with, if any? program on healthy aging and late life brain disorders

Unaffiliated Personnel

List investigators, if any, who will be participating in this protocol but are not affiliated with New York State Psychiatric Institute or Columbia University. Provide: Full Name, Degrees and Affiliation.

[name] (SUNY Stony Brook)

[name] (SUNY Stony Brook)

Application for Continuation of Research

Status

Current Status of Study:

All research interventions were completed. Only data analysis is ongoing.

Summary of Experiences to Date

Please provide a summary of scientific progress of the study and the experience of research participants, to date. This requirement is designed to allow for the investigator and the IRB to reassess the study's risks and benefits in terms of developments in the field, changing practice patterns, and new IRB policies and procedures.

36 subjects participated who were 75.3 ± 7.5 years old and 44.4% male. Significant, dose dependent increases in processing and gait speed were observed with L-DOPA (450mg dose: processing speed factor score effect size [ES] = 0.41, p = 0.001; dual task gait speed ES = 0.43, p = 0.003). [11C]raclopride Δ BPND was significantly different from 0 in sensorimotor (t = -4.85, df = 24, p < 0.001) and associative striatum (t = -2.52, df 24, p = 0.019) but not in limbic striatum (t = 0.265, df = 24, p = 0.793). Depressive symptoms decreased significantly on the Hamilton Rating Scale for Depression (ES = -0.4, p = 0.01). Drop-out rate was 8.3%, and nausea was the most frequently-reported side effect. By enhancing availability of dopamine, L-DOPA improved processing and gait speed in depressed older adults and significantly decreased [11C]raclopride binding in selected striatal subregions.

Funding

Have there been any changes in funding status since the prior approval?

No

Have the principal investigator and other investigators made all required disclosures of financial interest in the study sponsor/product?

Yes

Summary

Have there been any study findings, recent literature, or untoward events occurring here or at other sites in the past year which might affect the analysis of the safety, risks or benefits of study participation? No

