Hypothesis 2: 150mg, 300mg, and 450mg L-DOPA will increase processing and gait speed, with greatest improvement occurring at the 450mg dosage level.

Exploratory aims: To obtain information on the dosing and tolerability of L-DOPA in our patient population as well as identify PET and MRI biomarkers associated with slowing.

Description of Subject Population

Sample #1

Specify subject population

adults aged >59 years with a depressive disorder, decreased processing speed, and decreased gait speed Number of completers required to accomplish study aims

48

Projected number of subjects who will be enrolled to obtain required number of completers

Age range of subject population 60 years or older

Gender, Racial and Ethnic Breakdown

On the basis of previous depression studies conducted in the Adult and Late Life Depression Research Clinic, it is anticipated that the sample will be composed of 60% women and 40% men as well as approximately 75% Caucasian, 15% African American, and 10% Hispanic subjects.

On the basis of previous depression studies conducted in the Adult and Late Life Depression Research Clinic, it is anticipated that the sample will be composed of 60% women and 40% men. Description of subject population

This phase will enroll 60 outpatients who (1) are aged \geq 60 years, (2) diagnosed with Diagnostic and Statistical Manual (DSM) 5 (107) MDD, Dysthymia, or Depression Not Otherwise Specified (NOS), (3) have Center for Epidemiologic Studies-Depression Rating scale (CES-D) (108) score \geq 10, (4) have decreased gait speed (defined as average walking speed over 15' course \leq 1m/s), and (5) are willing to and capable of providing informed consent and complying with study procedures.

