- 21. The following measures will be collected weekly throughout the study: 24-item HRSD, CGI Severity and Improvement, Structured Pill Count Interview, Unified Parkinson's Disease Rating Scale (UPDRS) (questions 32 and 33 will be used in this study to assess the duration and disability of dyskinesias caused by L-DOPA), Treatment Emergent Side Effect Scale, and Inventory of Depressive Symptoms—Self Report (IDS-SR).
- 22. In addition, processing and gait speed assessments will be performed weekly at 1pm to control for time of day effects and the duration since the last morning L-DOPA dose (anticipated to be 4 hours). Processing speed will be assessed using the Digit Symbol test from the Wechsler Adult Intelligence Scale-III (WAIS-III) (119) and the Pattern and Letter Comparison tests (120). These tests are all reliable and valid, with moderate to high loadings on the latent speed factor. A latent factor (and subsequent factor score) will be extracted from the 3-test battery pre- and post-treatment and used as the main outcome in the R61. By extracting a latent factor and factor loadings we will utilize a more pure measure of processing speed than if we used the raw scores from an individual test or a sum total score from the three raw scores combined (121-124).
- 23. Gait will be assessed as both a single and dual task (ST, DT) on a 15' walking course in the LLDC. For the ST, patients are instructed to walk at their usual or normal speed over the 15' walking course. For the DT, patients are instructed to walk at their usual pace while simultaneously verbally listing as many animals as possible (fluency DT). In addition, a counting DT will be used in which patients are instructed to walk at their usual pace while simultaneously performing serial subtractions by threes starting at 100 (125). Patients will start and end at a point 2 meters from beginning of the 15' course to eliminate acceleration and deceleration effects. Each ST and DT will be assessed two times with the average used in the analyses. The ST assessment of walking speed in m/s will be used as the primary outcome measure for this study.

End of study procedures

24. Following the 3 week duration treatment study, endpoint assessments will be made. Patients will enter 3 month open treatment period provided free of charge as described below.

You can upload charts or diagrams if any

Criteria for Early Discontinuation

Criteria for Early Discontinuation

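### Single-task walking speed is the declared primary gait outcome, but the results summary supports its general gait conclusion only with an unnamed dual-task figure

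*Combined protocol and SAP*

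**What the plan says.** **Declared outcomes.** Study Procedures, Assessments, item 23 sets up a single-task walk and a dual-task walk with animal naming, and then a third condition: "In addition, a counting DT will be used", with serial subtraction. It closes: "The ST assessment of walking speed in m/s will be used as the primary outcome measure for this study". Item 22 separately describes a processing-speed factor score, "extracted from the 3-test battery pre- and post-treatment and used as the main outcome in the R61". Single-task speed is therefore the only gait measure called primary, alongside a cognitive measure called main.

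**Doses and covariate.** Hypothesis 2 in Specific Aims and Hypotheses reads: "150mg, 300mg, and 450mg L-DOPA will increase processing and gait speed, with greatest improvement occurring at the 450mg dosage level". Clinical treatment, item 17 says that weekly testing will show the effect on gait at each dose. Assessments, item 20 says that weekly pain scores will be "used as a covariate in analyses of gait speed".

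**Results.** Summary of Experiences to Date, in the Application for Continuation of Research, states: "Significant, dose dependent increases in processing and gait speed were observed with L-DOPA". A parenthesis then gives two values at 450mg: the processing-speed factor score (ES 0.41, p = 0.001) and "dual task gait speed ES = 0.43, p = 0.003". The closing sentence says that "L-DOPA improved processing and gait speed in depressed older adults".

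**SAP.** The Statistical Analysis plan refers to gait speed without saying which condition is meant.

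**The concern.** The plan picked one of three gait conditions in advance, and the summary prints a figure for a different one. The conditions are not interchangeable. All are walked at the patient's usual pace, but the dual tasks add a cognitive load, so a dual-task gain may partly reflect better handling of that load. A gain there does not establish a gain in undivided walking.

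Undivided walking is also the measure that defined these patients as slow: Evaluation, item 4 requires a speed below 1 m/s on a walk with no second task. A reader who takes the summary's conclusion at face value will assume that this measure improved. If the final report follows the summary, the trial will claim a gait benefit without showing its declared gait outcome, and the protection of naming that outcome in advance is lost.

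**Working it through.** The point is textual, so the check sets the declared measure beside the reported one.

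| Item | Declared | Given in the results summary |
|---|---|---|
| Main cognitive outcome | Processing-speed factor score (Assessments, item 22) | ES 0.41, p = 0.001 at 450mg |
| Primary gait outcome | Single-task speed, m/s (Assessments, item 23) | No value at any dose |
| Fluency dual task | Measured, not called primary (item 23) | Possibly the 0.43; not stated |
| Counting dual task | Measured, not called primary (item 23) | Possibly the 0.43; not stated |

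1. *Is single task replaced as primary anywhere?* No. The SAP says only gait speed, and no other section changes the choice made in item 23.

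2. *Is a single-task result given anywhere?* No. The three doses in Hypothesis 2 therefore have no single-task estimate among them.

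3. *Could the 0.43 include single task?* Its label says dual task. It may be fluency, counting or a combination of the two, but it is not the single-task walk.

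4. *Can the reported figure be reproduced?* No. The analysed number, the model and the SD used to scale the effect size are not given. Whether ES 0.43 with p = 0.003 follows from the test named in the SAP is a separate question, and nothing here relies on it.

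5. *Is the problem chance selection among gait measures?* Treat the 0.003 as one of three gait tests at 450mg and apply Bonferroni: 0.003 × 3 = 0.009. At an assumed two-sided 5% level (the documents state no level), the dual-task result survives. The dual-task signal is not being disputed; what is missing is the single-task result.

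6. *Can the single-task effect be inferred?* No. It would need the single-task data, or at least its mean change and variability, and neither is in the documents.

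**The case against.** The summary is one paragraph answering an ethics-board continuation prompt, written while data analysis was ongoing. Nothing obliges that field to tabulate every outcome at every dose. Its opening sentence speaks of gait speed in general and may well cover single task, and the parenthesis gives one example per domain. On that reading, a conclusion confined to dual-task gait could understate the findings.

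Much of this stands. The paragraph's brevity explains why most results are absent, and its silence on the pain covariate is no evidence that the covariate was left out. Counting unreported combinations of condition and dose would not be fair either, because the documents do not fix how many gait comparisons were intended.

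Two things remain. For processing speed the example chosen is the declared main outcome; for gait it is a measure that was not declared primary. And the paragraph does more than report progress: it draws an efficacy conclusion about gait speed.

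A reader might go further and infer that single-task gait showed no effect, or that the primary outcome was switched after the data were seen. The documents support neither. A missing value is not a null value, and nothing shows when or why the dual-task figure was chosen.

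**Conclusion.** The concern holds as a reporting gap that should be fixed. The only gait measure declared primary has no reported value at any of three doses. The one gait figure given belongs to a dual task that is not identified, so the general conclusion about gait speed has no figure behind it on the declared measure. The size of any resulting overstatement is unknown: the single-task effect could be larger than, smaller than or similar to the dual-task one.

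This rests on two readings: that item 23 still governs, since no later text replaces it, and that the label on the 0.43 is accurate. Confidence is high on the textual mismatch. There is no basis for a view on what the single-task data show.

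**What to change.** In the remaining analysis and in any results report:

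1. Report single-task gait speed as the primary gait outcome at 150, 300 and 450mg against Week 0, in m/s with 95% confidence intervals, whatever it shows, using the pain covariate already planned in Assessments, item 20.
2. Name the dual task (or combination) behind ES 0.43, report the other dual task as well, and label dual-task results secondary. If the primary gait outcome was changed, document when and why.
3. Word the gait conclusion as dual-task gait speed unless the single-task estimate supports the broader statement.

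The cost is some tabulation and rewording; no new data are needed. The downside is that the gait claim may become less favourable.
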